11.1 Subject compliance

Participants randomised to surgery will be followed up by research nurses to ensure compliance. Surgery will take place within 4 weeks of randomisation. Telephone reminders from research nurses will be used to encourage participants to return study diaries while both telephone from the trial manager and postal reminders will be used to encourage participants to return study questionnaires.

11.2 Withdrawal of participants

Any participants wishing to withdraw from the study may do so at any time.

12 Interim analysis and data monitoring

12.1 Stopping of trial

Clinical trials frequently fail to achieve the optimistic sample size predicted in study protocols. We have made conservative estimates of recruitment in this study. It is therefore likely that we will achieve sample size faster than estimated. We will identify with the Programme Manager agreed criteria for the shortening or premature stopping of the trial in the event that recruitment to the trial is quicker than estimated or falls below 60% in the second and third quarters of recruitment in each area. In the event of a site failing to achieve an agreed minimum recruitment within six months, it will be closed down and an additional centre(s) recruited.

12.2 Monitoring, quality control and assurance

The study has a Trial Steering Committee which meets 6 monthly and consists of [name], External Member, [name], Principal Investigator, Emeritus [name], External Member, [name], Consultant, [name], Consultant, [name], Investigator, [name], Research Nurse, [name], Consultant, [name], Trial Manager, [name], Independant Statistician, [name], Research Nurse, [name], Consultant, [name], Research Nurse, [name], Statistician, [name], Research Nurse, [name], External Member, [name], Principal Clinical Investigator, [name], Trial Administrator, and [name], Consultant. The Trial Steering Committee is responsible for monitoring public interest and ensuring issues relating to research governance are met.

The trial does not have a data monitoring committee since it examines routine therapies.

The Principle Investigators will be responsible for the day-to-day study conduct at site. The Trial Manager will provided day-to-day support for the sites and provide training through Principle Investigator meetings and site initiation visit.

The Trial Manager will ensure that the study in conducted in accordance with GCP through a combination of central monitoring and site monitoring visits.

Consumer involvement will be encouraged and facilitated throughout the study by the establishment of a consumer advisory panel. We will use the advisory panel to help clarify important outcomes for children and their parents (or carers) and to assist in the development of participant-oriented data-collection methods. By consumer we include here children and their parents as well as representatives of appropriate advocacy groups such as the Patients Association. Our experience of consumer panels in the development and implementation of other studies (e.g. quality of life of people with dementia and treatment for primary biliary cirrhosis of the liver) have highlighted the different types of involvement and the different ways that consumers can be involved in primary research. Parents and children will be involved in an

advisory capacity rather than in a full participatory role. We will establish and convene regularly the consumer advisory panel in which the group process will use focus group methods. Throughout the project (at least annually) we will use the advisory panel to voice participants' concerns and to identify participant-oriented solutions to such concerns.

12.3 Assessment of safety

Adverse events will be recorded by self completion daily diaries (parent or child) which will be collected four weekly and GP records which will be examined at the end of the 24 months follow up period. Expected adverse events include infection, haemorrhage and pain following tonsillectomy with possible hospital readmission as well as sore throat, nausea, fever and dysphagia.

For the purposes of this study no reporting of serious adverse events is required. All adverse events will be managed as per normal care, since the intervention process of this study does not deviate from normal care.

13 Ethical considerations

The conduct of this study will be in accordance with the ethical principles set out in the Declaration of Helsinki.

The trial has approval from MREC and all the associated LRECs. The trial also holds a Clinical Trial Authorisation from the MHRA. The trial has NHS R&D and Caldicott Guardian approval from each participating site. There are no particular ethical problems with this trial. The ethical challenge is as with any surgical randomised trial where one arm is an irreversible procedure under general anaesthesia and the other limb effectively maintenance of the status quo with reverting to surgery an outstanding choice. Set against the surgical risk, however, is the essentially 'curative' nature of the intervention – no tonsillitis can occur once the tonsils have been removed. Further, the children under consideration all have qualifying levels of sore throat and would otherwise be eligible for surgery. In other words the issue is more the withholding of tonsillectomy rather than one of random allocation to intervention.

All subjects will provide written informed consent before any study procedures are carried out and a participant information sheet will be provided. As part of the consent process participants must agree to researchers & regulatory representatives having access to their medical records. Participants will also be informed that they have the right to withdraw from the study at any time.

14 Financing and insurance

The NHS Trust has liability for clinical negligence that harms individuals toward whom they have a duty of care. NHS Indemnity covers NHS staff and medical academic staff with honorary contracts conducting the trial.

15 Reporting and dissemination

Amended from children (or carers) reporting experience of mild symptoms, 6 or more episodes within 2 years or 8 or more episodes within 1 year, and children reporting experience of moderate symptoms (sore throat for 5 days or more), 6 or more episodes within 2 years or 6 or more within 1 year to children (or carers) reporting experience of 4 or more episodes of sore throat within each of 2 years or 6 or more episodes of sore throat within 1 year. In order to increase recruitment to the trial. (May 2004)

Exclusion criteria

Amended from children will be excluded if they require hospitalisation due to tonsillitis or quinsy; have obstructive symptoms suggestive of clinically significant sleep apnoea syndrome or rare medical conditions such as glomerulonephritis or Henoch Schonlein purpura; or have previously had a tonsillectomy; or have suspected velopharyngeal insufficiency to Children will be excluded if they require hospitalisation due to quinsy; have obstructive symptoms suggestive of clinically significant sleep apnoea syndrome, have rare medical conditions such as glomerulonephritis or Henoch Schonlein purpura; have previously had a tonsillectomy; have suspected velopharyngeal insufficiency, have co-morbidity that means they are unable to undergo the operation within the next 6 months, have a bleeding disorder, or have congenital/valvular heart disease in order to increase safety. (May 2004)

Setting

Two additional centres Yorkhill Royal Hospital for Sick Children, Glasgow and Bradford Royal Infirmary added. (September 2004)

Project timetable

Extension of the project from 5 to 7 years following poor patients recruitment. (July 2004)

Data monitoring

A Trial Steering Committee was formed. (January 2004)

Measuring participants' preferences and utilities

Details regarding this sub study were added as Appendix 2. (March 2006). Amendments were made to this sub study following pre-pilot work (November 2007)

Data to be collected

Postal questionnaires become interview administered. (October 2006)

Sponsor

Sponsor changed from Department of Health to Newcastle upon Tyne Hospitals NHS Foundation Trust. (August 2007)

Study Centre

The Centre for Health Services Research, University of Newcastle upon Tyne became The Institute of Health and Society, Newcastle University. (October 2006)

Appendix 2: Measuring participants' preferences and utilities

Background

Recurrent sore throats and tonsillitis are commonly experienced in childhood (98.7%), with the majority of children having more than 4 episodes of sore throats annually¹. There is currently no clear evidence on the best treatment option for recurrent sore throats and tonsillitis. Current treatments include pharmacotherapy or surgery. Parents of children who have undergone tonsillectomy tend to report a net improvement in children's condition, even though systematic reviews of the few clinical studies conducted so far do not show any significant clinical improvement in terms of severity and frequency of infections^{2;3}. The literature has highlighted that parental enthusiasm for tonsillectomy is dictated by their perceived improvement in healthrelated quality of life dimensions, such as behaviour, general wellbeing, growth and sleep⁴. Very little empirical data is available on preferences for health states related to sore throats and tonsillitis. Given the high prevalence, morbidity rates and conspicuous resource implications at both NHS and individual levels, the issue of improving insights into the sets of outcomes on which to base treatment decisions becomes of public health relevance. Investigators have highlighted the need to inform parents about the clinical effectiveness of tonsillectomy, and to obtain their informed values about the (perceived) benefits of the procedure weighted against its morbidity³. The measurement of parents' preferences for alternative non-surgical management and likelihood of adverse events is also important.

Objectives

- To establish the optimal treatment strategy from the perspective of parents in terms of their expected utility, and to determine to what extent this is preferred over its alternative;
- To ascertain whether and to what extent the (dis) benefits elicited from parents for tonsillitis is affected by the number of recurrent episodes (and their duration);
- To ascertain whether the parental decision making process is different from the one expressed by older children and, if yes, why and to what extent they are different;
- To provide insight into informed and shared medical choice models.

Methods

Older children's and carers' values will be used to elicit preferences for trade-off between the perceived risks and benefits of surgery versus drugs treatment for sore throats and tonsillitis. Preferences will relate to scenarios associated with morbidity and quality of life because of symptoms and treatment complications. The scenarios are based on the health outcomes and quality of life domains relevant to the problem. Interviews will be carried out with a sample of older children and carers from 2 of the otolaryngology departments (Newcastle and Glasgow) and the Standard Gamble method⁵ will be used to derive utilities weights.

The Standard Gamble Method

Standard gamble is a technique used to elicit individuals' preferences. It is based on the axioms of expected utility theory⁶ which therefore means we are measuring preferences under uncertainty. Standard gamble can be used to measure health state preferences for chronic or temporary health states. For chronic health states individuals are asked to value living with a health state for the rest of their lives. For a temporary health state individuals are asked to value living with a health state assuming they had to live in it for a specified period of time. To measure individuals' preferences for a chronic health state they are offered a choice between two alternatives. Alternative 1 is some form of treatment that has two possible outcomes; a return to full health for the rest of their life or immediate death. Alternative 2 is a certain outcome of remaining in the chronic health state for the rest of your life.

The standard gamble method of preference elicitation can be difficult for many people to understand as most people do not usually express their preferences in terms of probabilities. For this reason when conducting the interviews a visual aid known as a chance board can be used⁵. The chance board is used to present to people probabilities of 2 uncertain outcomes and 1 certain outcome. The board is divided into 2 sections. The top half of the board illustrates the uncertain Choice A (Alternative 1) with probability, p, of the most preferred health state and 1-p of the least preferred health state. Two small windows in this part of the board show what p and 1-p are. The probabilities can be changed by turning the wheel underneath the board. On the bottom part of the board is the certain outcome Choice B (Alternative 2). The health state placed in this section relate to symptoms which characterise tonsillectomy. The chance board converts the probabilities in to a percentage risk of an event (return to full health, immediate death or health state i) occurring. This is more understandable to most people. To begin with the chance board is set at a 90% chance of the preferred health state (returning to full health) and a 10% chance of the least preferred health state (immediate death). The individual then makes a choice between Choice A or Choice B. The probabilities are then altered using a ping-pong strategy, this is where the probabilities are alternated back and forth between a low value and a high value until the individual is indifferent between Choice A and Choice B. Using a ping-pong strategy reduces the possibility of anchoring bias. It also reduces the risk of a framing effect caused by the individual believing the increases or decreases in probability are gains and losses subject to a reference point. The percentages on the chance board convert to the probabilities for p and 1-p. The probability at the point where the individual is indifferent between Choice A and Choice B is the utility value of the health state described in Choice B.

As standard gamble is based on expected utility theory it is the preferred technique for preference elicitation by many economists. It has been claimed that uncertainty in the decision making process mirrors the clinical decision making process where doctors and patients must make choices under uncertainty⁷. However it could also be argued that the decision making process in health care is much more complicated than that described by a simple standard gamble question where there are only 2 outcomes and it is centred around full health and death. In a typical clinical decision there will be multiple outcomes with less wide ranging effects than full health and immediate death. The standard gamble method has a number of problems associated with it. The main problem is that it is cognitively demanding as many people are not familiar with expressing their preferences as probabilities. Therefore it may produce results which do not match individual's true valuations. Also many people are risk averse when it comes to their health and so will always choose to remain in state i (the certain outcome) no matter how bad it may be rather than take the gamble. This has lead to higher reported utility values for standard gamble compared with valuations produced by time trade off and the visual analogue scale.

Study sample

The sample will consist of consenting participants from 2 of the otolaryngology departments (Newcastle and Glasgow).

Inclusion criteria for children:

- Children aged 12 to 15
- Any gender
- Any nationality (interpretation services will be sought where appropriate)
- Experience of at least one episode of sore throat in the last 12 months, which required medical attention

Inclusion criteria for parents/carers:

- One of the parents (or carers) of children aged between 4 and 15 years, who had experience of at least one episode of sore throat in the last 12 months, which required medical attention
- Any age
- Any gender
- Any nationality (interpretation services will be sought where appropriate)

Exclusion criteria for children/parents: Unable to communicate Learning difficulties

The aim is to elicit utilities from the perspective of the parents, since they are the medical decision-makers for the child⁸. We assume that within a parental relationship, the 'principal-agent' model holds, i.e. the parents prefer the treatment which they believe to be in their child's best interest. Sensibly, we assume that children do not have a clear discernment between alternative treatments and outcomes, and therefore they will unavoidable rely on their parents' decisions. However, since older children (12+) are more mature and have more capabilities to make abstract thoughts and use complex language⁸, their utility values will also be elicited, and compared with those of the parents. This will allow us to test the agency model against the alternative hypothesis that parents aim to maximise their own utility function, including, in addition to the arguments of the child's utility function, factors such as the impact of the disease on the use of their own time and emotional status⁹, or the satisfaction of their own deep psychological needs¹⁰.

Sample size and recruitment process

A sample of 100 parents and 100 older children from 2 of the otolaryngology departments (Newcastle and Glasgow) will be telephoned and asked whether they will be willing to take part in the utility study. Interviews will take place at a mutually convenient place and time after the agreed course of treatment.

Development of scenarios

Scenarios describe the relevant outcomes. The process of scenario building is informed by the type of events, duration/frequency of events. This information has been derived from a review of the literature. Scenarios are outlined below.

The interview process

An interviewer's handbook and response booklet (i.e. a response marking form) have been prepared and are enclosed together with a consent form and information sheet. Interviews will be initially pre-tested with IHS staff, therefore a pilot study will be conducted before the main study on 4 or 5 pairs of parents and children aged 12-16. Interviews from the pilot study will be checked to ensure quality and standardisation of the interview process. Interviews for the pilot and main study will not be taped.

Analysis strategy

Data will be collected on the utility scores of two health states estimated using standard gamble. Basic demographic data will be also be collected. Frequencies of the structure of the sample such as the male/female ratio and parent/own value ratio will be produced along with frequencies of the characteristics of the respondents such as stage of illness and socio economic status. The mean age of the sample will also be estimated. The mean utility values for each of the health states estimated using standard gamble will be calculated for the whole of the sample.

References

- 3. Marshall T. A review of tonsillectomy for recurrent throat infection. *Br J Gen Pract* 1998; **48:** pp 1331-1335.
- 4. Wolfensberger M, Haury J-A, Linder T. Patient satisfaction 1 year after adenotonsillectomy of their children. *Int J Pediatr Otorhinolaryhgol* 2000; **56**:pp 199-205.
- 6. Von Neumann, J. and Morgenstern, O. Theory of games and economic behaviour. 1944. Princeton University Press, Princeton, NJ.
- 7. Gafni, A and Birch, S. Preferences for outcomes in economic evaluation: An economic approach to addressing economic problems. *Social Science Med*_1995;**40**:767-776.
- 8. Stewart MG. Paediatric outcomes research: development of an outcomes instrument for tonsil and adenoid disease. *Laryngoscope* 2000; **Suppl.94**: pp 12-15.

NESSTAC Scenarios for utility study [for parents]

Health state X

Your child gets 6-7 sore throats each year. These last 7 to 10 days each.

During this time your child...

- finds it hurts to swallow
- has a temperature, headache, earache
- feels sick and eats less.
- takes antibiotics and pain killers which may give them diarrhoea and a skin rash. After the first 5 days these symptoms begin to improve.
- has time off school, when they go back they are behind with the work.
- cannot take part in family, group or sporting activities.
- feels ill and is tired and irritable and may argue with you and your family.
- You are worried about them and may not be able to go to work or carry out your normal activities.

Health State Z

For up to 2 weeks after the treatment your child...

- Has a sore throat
- Feels sick
- Has a temperature
- Tired and irritable
- Small risk (1 in 20) that the tonsils will bleed and they have to have a blood transfusion
- Cannot go to school
- Cannot take part in family, group or sporting activities
- May wake up in the night
- You are worried and have to stay off work to look after them

After the first 2 weeks your child....

- Has 1-2 sore throats each year. These last 2-3 days each
- Has 2-3 days off school each year when they have a sore throat
- Feels ill and is tired and irritable when they have a sore throat
- You may have to take time off work when they have a sore throat
- When they do not have a sore throat your child has no pain or discomfort, behaves normally and can take part in their normal activities.

Good health

Your child...

has no pain or discomfort and is full of energy.

- behaves normally at home and school.
- can go to school and join in classes
- is able to join in family, group or sporting activities.
- You have no worries about their health. You are able to carry out your normal activities.

NESSTAC Scenarios for utility study [for 12-15 year olds]

Health state X

• You get 6-7 sore throats each year. These last 7-10 days each.

During this time...

- It hurts to swallow
- You have a temperature
- Headache
- Feel sick and eat less
- Take antibiotics which can give you diarrhoea and a rash
- You feel tired and irritable
- Cannot go to school
- Cannot do your usual activities
- Your parents are worried about you and may not be able to go to work.

Health State Z

For up to 2 weeks after the treatment you ...

- Have a sore throat
- Feel sick
- Have a temperature
- Feel tired and bad-tempered
- Small risk (1 in 20) that the tonsils will bleed and you have to have a blood transfusion
- Cannot go to school
- Cannot take part in family, group or sporting activities
- May wake up in the night
- Your parents are more worried and have to stay off work to look after you

After the first 2 weeks you

- Have 1-2 sore throats each year. These last 2-3 days each
- Have 2-3 days off school each year when you have a sore throat
- Feel ill and tired and bad-tempered when you have a sore throat
- You parents may have to take time off work when you have a sore throat
- When you do not have a sore throat you have no pain or discomfort, behave normally and can take part in your normal activities.

Good health

- no pain or discomfort and you are full of energy.
- behave normally at home and school.
- able to go to school and to join in classes
- join in family, group or sporting activities.
- Your parents go to work and carry out their normal activities.

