9.1.1.6 Sensitivity analysis

To handle uncertainty not related to sampling variations and to enhance the generalisability of the results, one-way; multi-way and extreme scenario analysis will be undertaken as appropriate and confidence intervals for cost-effectiveness ratios will be estimated under different scenarios ⁴³. A sensitivity analysis taking into account differences in resource use which are practically significant (i.e. potentially costly) but which have not been shown to be statistically significant, will also be undertaken. The sensitivity analysis will also make explicit all the simplifying assumptions made to collect the data⁴⁴.

The application of discounting to the benefits will also be tested in the sensitivity analysis, as well as a range of discount rates. Particular attention will also be given to whether the costs data used reflect the true marginal opportunity costs of the resources used. When more than one reliable source of information is available, such data will be used as a term of comparison. The use of different costing methods for multi-centre studies will be explored.

Earlier studies²⁸⁻³¹suggest that longer term outcomes such as reduction in recurrent sore throat may show only marginal benefits. An equivalence trial with a substantially larger sample size would be necessary to capture significant longer-term outcomes. To contain the cost of the trial we have not proposed a three year follow up. However, the future sequence of clinical events and economic impact will be modelled beyond 2-year follow-up. The relevant data will be derived from studies which will be available and experts' opinions.

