10.2 Statistical analysis

10.2.1 Main analysis

An intention to treat analysis will be performed. In particular, children randomised to nonsurgical conventional medical treatment will be retained in that group for the analysis even if they subsequently receive a tonsillectomy.

The primary clinical outcome measure will be the number of episodes of sore throat. This variable will be analysed using generalised linear modelling assuming a Poisson error structure with a log link function⁵¹. By fitting the difference between the two experimental groups as a fixed effect, interval estimates of the effect of tonsillectomy (in each of the first two years of follow up) will be generated. These estimates will then be used in the economic analysis.

The same approach will be used to analyse the other outcomes. A Poisson error structure will be assumed for data in the form or a count (such as the number of episodes of absence from school) and normal error structure adopted for continuous variables (such as the quality of life indices).

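### The utility sub-study's stated analysis pools parents with older children and names no contrast between health states, so the extent of parents' preference gets a mixed figure with no interval

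*Protocol*

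**What the plan says.** Protocol Appendix 2, Objectives, first item: the sub-study is to establish which treatment strategy is best in expected-utility terms as parents see it, and "to determine to what extent this is preferred over its alternative". The Study sample section repeats that utilities are sought from the parents' viewpoint, because parents make the decision. It adds that for children aged 12 and over "their utility values will also be elicited, and compared with those of the parents".

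Sample size and recruitment process: "A sample of 100 parents and 100 older children from 2 of the otolaryngology departments" will be telephoned and invited to take part.

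Analysis strategy: "Data will be collected on the utility scores of two health states estimated using standard gamble". The paragraph then lists frequencies describing the sample (including the balance of parent and own-value respondents) and mean age. It ends: "The mean utility values for each of the health states estimated using standard gamble will be calculated for the whole of the sample".

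The scenario pages contain states X and Z in both the parents' version and the version for 12-15 year olds. X is 6-7 sore throats a year. Z is up to two weeks of recovery and then 1-2 sore throats a year.

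Two other places in the protocol speak of intervals or models. Section 10.2.1 deals with differences between the randomised groups, with a "normal error structure adopted for continuous variables (such as the quality of life indices"). Section 9.1.1.6 says that "confidence intervals for cost-effectiveness ratios will be estimated under different scenarios".

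**The concern.** The extent to which parents prefer one strategy over another is a contrast between two values given by parents. The stated output falls short of that in two ways.

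First, a mean over the whole sample averages parents with older children. The first objective is about parents. The third objective asks whether older children decide differently, and a pooled mean hides exactly that.

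Second, the output is two separate means. No difference between the states is named, and no SD, standard error or interval. Neither section 10.2.1 nor section 9.1.1.6 fills the gap: one concerns randomised arms and the other cost-effectiveness ratios. The planned comparison of children with parents is a different contrast again.

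Followed as written, the sub-study would report a figure for the wrong mix of respondents and could not say how precisely the preference is known. Anyone who built an interval from the two published means would have to treat them as independent samples, although the same people probably gave both values.

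**Working it through.** **Is there a figure to reproduce?** No. The sub-study states no SD, effect size, power or precision target for its 100 and 100. The checks below show what the stated output can and cannot deliver.

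**Step 1: the point estimate.** If every respondent values both states, mean(Z) - mean(X) = mean(Z - X). The point difference can therefore be recovered from the two planned means. If some respondents value only one state, the two means refer to different people and the identity fails.

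**Step 2: whose difference it is.** With nP parents and nC children, pooled difference = (nP × dP + nC × dC) / (nP + nC), where dP and dC are the mean differences in each group. At 100 and 100 this is (dP + dC)/2, so it misses the parents' value by (dC - dP)/2. Illustration with assumed values: dP = 0.10 and dC = 0 give a pooled difference of 0.05, half the parents' figure. With dC = 0.10 there is no error. The protocol gives no basis for choosing between these.

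**Step 3: the interval.** For n respondents who value both states:

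- paired SE = sqrt[(s1² + s2² - 2 r s1 s2)/n]
- SE if the two means are treated as independent = sqrt[(s1² + s2²)/n]
- 95% half-width = 1.96 × SE

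The planned output contains neither s1 and s2 with r, nor the SD of the differences, so the interval cannot be computed from it.

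**Step 4: size, equal SDs.** Assumptions: s1 = s2 = SD between 0.10 and 0.30, r between 0 and 0.7, n = 100 parents. The paired SE becomes SD × sqrt[2(1 - r)/n]. Worked case, SD 0.20 and r = 0.5: SE = 0.20 × sqrt(1/100) = 0.020 and half-width = 0.039. Ignoring pairing: SE = 0.20 × sqrt(2/100) = 0.028 and half-width = 0.055.

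| SD | Pairing ignored | r = 0.3 | r = 0.5 | r = 0.7 |
|---|---|---|---|---|
| 0.10 | 0.028 | 0.023 | 0.020 | 0.015 |
| 0.20 | 0.055 | 0.046 | 0.039 | 0.030 |
| 0.30 | 0.083 | 0.070 | 0.059 | 0.046 |

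The narrowing is 1 - sqrt(1 - r): 16% at r = 0.3, 29% at r = 0.5 and 45% at r = 0.7.

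**Step 5: unequal SDs.** In general the narrowing is 1 - sqrt[1 - 2 r s1 s2/(s1² + s2²)]. Since 2 s1 s2/(s1² + s2²) is at most 1, unequal SDs reduce the gain at any positive r. With assumed SDs of 0.10 and 0.25 and r = 0.5: s1² + s2² = 0.0725 and 2 r s1 s2 = 0.025. The ratio is sqrt(0.0475/0.0725) = 0.81, so the narrowing is about 19%, not 29%.

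**Step 6: fewer interviews.** The 100 parents are the number invited. If 50 are interviewed (assumed), SD 0.20 gives a half-width of 0.078 with pairing ignored and 0.055 paired at r = 0.5.

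**The case against.** The best defence is that the paragraph is short and descriptive. It does not say that nothing else will be computed, it prescribes no unpaired test, and the comparison of children with parents appears elsewhere in Appendix 2 without being repeated there. An SD, an interval or a paired contrast could be left to a statistical analysis plan. The objective asks for an extent, not for an interval. The utilities may also feed the cost-utility analysis, where sensitivity analyses and intervals for ratios are planned.

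Part of this stands. A reader might infer that the sub-study cannot estimate the preference at all; step 1 shows that with complete data it can. A reader might also infer that the plan fixes an independent-samples analysis; it fixes none. That each respondent values both states is likely from the scenario pages, but no sentence says so, and the interviewer's handbook and response booklet are not in the text. An interval that wrongly ignores positive correlation would be too wide, so that error is on the cautious side.

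What does not stand is that this is only missing detail. Appendix 2 has its own Analysis strategy, and the estimate stated there is for the whole sample, whereas the objective is about parents. That is a stated choice which does not match the stated aim, and nothing elsewhere in the protocol supplies a contrast of Z with X. Intervals for cost-effectiveness ratios do not give one for the utility difference.

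**Conclusion.** The point holds as a minor one. The stated analysis delivers one mean per state over parents and older children together; the first objective needs a contrast among parents, with its precision. The point difference is recoverable from the planned means if data are complete, but for the wrong mix of respondents and without an interval.

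The mismatch with the parents' perspective follows from the text alone. The gain from pairing does not. The range of 16% to 45% assumes equal SDs and correlations of 0.3 to 0.7, and unequal SDs lower it. It is tempting to say that pairing is worth a doubled sample. That is true only at r = 0.5 with equal SDs, and the protocol supports neither figure. The half-widths for n = 100 also assume that every invited parent is interviewed and values both states.

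The trial's primary outcome, its sample size and the comparison of randomised arms are not affected.

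**What to change.** In Appendix 2, Analysis strategy, replace the whole-sample summary with the following:

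- Report utilities separately for parents and for older children, with the mean and SD of each state as description.
- For the first objective, use parents who valued both states. Give the mean within-respondent difference, utility(Z) minus utility(X), with a 95% confidence interval (paired t, or a bootstrap over respondents if values are skewed near 1). Also give the share of parents who value each state higher.
- Report how many respondents were invited, how many were interviewed and how many valued both states.
- State that reading Z minus X as a preference between strategies assumes that the two scenarios adequately represent those strategies.

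The cost is a few sentences. If each interview covers both states, as the scenario pages imply, no new data and no further interviews are needed. Writing this down before the utilities are analysed also avoids choosing the contrast after seeing the results.
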